#### 4) Inclusion and Exclusion Criteria

Inclusion criteria: A subject will be eligible for study participation if subject meets all following criteria:

- 1. Subject has Fragile X syndrome with a molecular genetic confirmation of the full FMR1 mutation (>200 CGG repeats) or the other loss of function mutations of the FMR1 gene (SNVs and deletions of the gene).
- 2. Subject is a male or non-pregnant, non-lactating female age 6 through 35 years, inclusive.
- 3. Subjects who are capable of becoming pregnant must use an acceptable method of birth control for the duration of the study. Acceptable forms of birth control include abstinence (only for subjects who are not sexually active), intrauterine devices in place for at least 3 months, oral contraceptives, surgical sterilization, or adequate barrier methods.
- 4. Subject must have a caregiver (parent, guardian, or other legally authorized representative) who is willing to participate in the whole study.
- 5. Subject and caregiver are able to attend the clinic regularly and reliably.
- 6. Subject and/or subject's caregiver is able to understand, read, write and speak English or French fluently to complete study-related materials.
- 7. For subjects who are not their own legal guardian, subject's caregiver is able to understand and sign an informed consent to participate in the study.
- 8. The use of concomitant medication must be stable, in terms of dose and dosing regimen, for at least 4 weeks prior to Screening and must remain stable during the period between first visit (Screening) and the commencement of the study; every effort should be made to maintain stable regimens of allowed concomitant medications from the time of commencement of double-blind study medication until the last study assessment.
- 9. Behavioral/educational treatments must be stable for 4 weeks prior to first visit (Screening) and must remain stable during the period between Screening and the commencement of randomized double-blind study medication.

10. Overall age equivalent is not higher than 13 and IQ is not higher than 85, as assessed at Screening on the Leiter-III, and subject must speak at least occasional 3-word phrases.

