#### Treatment Measures:

Expressive Language Sampling (ELS) - Expressive language samples will be collected from each participant twice, at study baseline and at the end of treatment/week 16. At each assessment, samples will be collected in two different contexts: conversation and narration. In conversation, the examiner engages the participant in talk on a variety of topics (e.g., school) according to guidelines that specify the order of topics and the ways in which topics are introduced and maintained. In narration, the participant tells the story in a wordless picture book. The examiner prompts and responses are scripted. In both contexts, the examiner follows a script that minimizes his/her participation, maximizes the participant's contribution, and avoids the use of examiner language that would constrain the participant's talk. In both conversation and narration, all talk is digitally recorded and transcribed by highly experienced transcriptionists following procedures that yield high intertranscriber agreement (Abbeduto et al., 1995). Computerized analyses of the transcripts characterize multiple dimensions of the talk produced by the participant (e.g., vocabulary diversity, syntactic complexity). The mean Number of Different Words (NDW) in conversation and in narration will be computed (and statistically adjusted through analysis of covariance for differences in talkativeness as suggested by Conners et al., 2018) and serve as the primary outcome measure. This measure has been shown to have excellent test-retest reliability, display negligible practice effects, be free of floor and ceiling effects, have good construct validity for individuals with FXS, and improve with treatment (Berry-Kravis et al., 2013; Channell et al., 2018; McDuffie et al., 2016). For French speaking participants, we will use a French translation of the ELS.

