Visual Analogue Scale (VAS) – Parents will mark on a visual line measuring 10 cm with one side marked "worst behavior" and the other side marked "best behavior." They will mark three key behaviors that we are targeting with this study: behavior problems (parents can note which problems are most severe and track on them throughout the study), language abilities, and eating behavior. For each behavior, they will mark their impression of the behavior at baseline and during the follow-up visits at week 8 and end of treatment/week 16. The horizontal marks are measure in centimeter distance where they fall from the worst behavior side so that we can see improvements or worsening of behavior over this time period.

Vineland Adaptive Behavior Scales—Third Edition (VABS-III) — The Vineland, which is a gold standard test for assessing adaptive behavior that is widely used in clinical trials, will be administered to the parent/caregiver at baseline and end of treatment/week 16. Subtests include Communication, Daily Living Skills, Socialization, Motor Skills, and Adaptive Behavior Composite. The Vineland has been normed for individuals with intellectual disability and ASD. The third edition includes updated item content to streamline similar items and reduce redundancy, to reflect changes in daily living (e.g., technology) and in conceptions of developmental disabilities (e.g., ASD), and to allow for potential cultural differences by using more generalized wording of certain items. French participants will perform the Vineland II Échelles de comportement adaptatif as version III is not available in French.

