### 8) Data and Specimen Management and Confidentiality

### Recruitment:

Subjects will be recruited through the FXS clinics at the University of Alberta and CHU Sainte-Justine as well as by referral from other centers in Canada. The University of Alberta site will also recruit patients from other centers across Canada (including in Alberta, Manitoba, Saskatchewan, and British Columbia) referred to the study. The Universite de Montreal site will also recruit patients from the Maritimes, Quebec, and Ontario referred to their center. This way, any FXS patient from Canada will be able to participate in the study if they want. Approved study information material will be posted on intellectual disability, autism, and FXS support group websites and social media feeds, and in clinical spaces.

Educational and scientific conferences by the Co-I to health professionals, education systems, and other individuals interacting with FXS patients and families will also be used to disseminate knowledge about the study and recruitment. A website for the study has been created with videos and testimonial from clinicians, researchers, patients, and family members to generate interest and facilitate recruitment.

Potential subjects/caregivers who are interested in participating in the study will be able to contact a study team member to schedule their visit 1. This will also allow potential subjects/caregivers to ask study-related questions and discuss the study in depth with the research team. The research team will use a pre-screen form where questions will be asked to the participant/caregiver over the phone to determine if the participant will be eligible to continue to visit 1. Informed consent will be signed at the first visit. Informed consent includes authorization to access and use their health information for the research study. For participants followed at CHU Ste-Justine, the study team is authorized to access medical records of CHU Ste-Justine patients to verify eligibility prior to getting their consent for the trial.

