WCHRI's REDCap installation is housed in a secure data centre at the University of Alberta Hospital and is behind the Faculty of Medicine & Dentistry's firewall. Data is entered through a web based interface using 128 bit SSL encryption. Login is via a username/password pair with additional two factor authentication (2FA). Additional information is available in WCHRI's privacy document (https://redcap.ualberta.ca/privacy.pdf).

Coordinators and investigators at each study site will only have access to data relating to their own study participants. Study management staff (PI and research coordinator) at the lead site will have access to data for all study participants. Staff at the WCHRI DCC will have access to data for all study participants. This access is required to perform system management functions, data cleaning, and analysis. Once the study database is "locked" and data has been extracted for analysis, read only access to the study database will be granted to the PI and/or their designate if requested.

We will have a material transfer agreement between the Canadian sites and a research institute in the United States (UC Davis MIND Institute) that plans to collect similar data, with the hopes that it may contribute to the research endpoints. This collaboration may include additional biomarker studies. With a material transfer agreement, each site may have access to blood epithelial cells cultured from urine and fibroblasts of patients at other sites for future research, if the patient consents to this use, in which case all such specimens would be de-identified upon transfer.

Analysis will be based on the intention-to-treat principle. The team at the University of Alberta, Ste-Justine, and MIND Institute will collaborate on data analysis. The data will be merged into one dataset shared and analyzed across the different sites. De-identified data will be shared across sites as stated in the consent form including the UC Davis and Ste-Justine forms. Data will

also be analyzed in the lab of [name] using machine learning approaches and advanced statistical analysis, as well as proteomics on urine samples.

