The analysis of treatment efficacy will be based on the analysis of covariance (ANCOVA) with outcomes (receptive and expression language at 4-month follow-up with corresponding baseline measure as a covariate). The chosen endpoint at 4-month, based on preliminary data, provides a reasonable treatment time period to assess changes in the response. The proposed method adjusts for potential baseline differences between treatment arms despite randomization, if any. The sample size/power for the ANCOVA is based on sample size needed for a t-test by a variance inflation factor 1-2 where there is the correlation between baseline and follow-up measures. From our preliminary data, the receptive and expressive scores have ranges from approximately 0.2 to 0.5. Thus, we predict power for the t-test and power for the ANCOVA will be higher depending on this factor. We estimate clinically relevant effects sizes, based on our preliminary data, at follow-up visit as follows (metformin/placebo): receptive language score mean 18.1/23.8, SD=7.0; expressive language score mean 13.6/20.7, SD=8.4. For these effect sizes of the 2 primary measures, the ANCOVA will have power of at least 80% (or have between 0.2-0.5) at level alpha=0.016 with the proposed total sample size n = 60 for each group (placebo and treatment).

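### The primary word count pools English and French samples but adjusts only for baseline; adding language of assessment to the ANCOVA would recover some precision at almost no cost.

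*Combined protocol and SAP*

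**What the plan says.** The combined protocol defines the primary outcome in section 7 (Treatment Measures, Expressive Language Sampling) as NDW averaged over conversation and narration, "statistically adjusted through analysis of covariance for differences in talkativeness". It adds: "For French speaking participants, we will use a French translation of the ELS".

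The analysis text is in section 8, under Confidentiality. On pooling it says: "The data will be merged into one dataset shared and analyzed across the different sites". The efficacy model is an ANCOVA on "receptive and expression language at 4-month follow-up with corresponding baseline measure as a covariate". No language term, site term, within-language scaling or check that English and French counts are comparable appears anywhere.

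Three other places bear on the point:
- Inclusion criterion 6 (section 4) requires that the subject and/or caregiver be "able to understand, read, write and speak English or French fluently", with no restriction by site.
- Section 8, Recruitment: "The Universite de Montreal site will also recruit patients from the Maritimes, Quebec, and Ontario referred to their center".
- Section 18, Randomization: allocation is run separately at each site and stratified by sex. Language is not a stratification factor.

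The plan does handle language for other instruments when they are administered. French participants take a different Vineland edition, "as version III is not available in French", and only the non-verbal NIH Toolbox tasks. No corresponding rule is given for analysis.

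**The concern.** NDW counts words, so its level may depend on the language spoken and on the version of the task. If French and English speakers differ in average NDW, a model with one intercept and one baseline slope treats part of that difference as noise. The standard error of the treatment comparison is then larger than it need be.

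A site term, which is not specified either, would not reliably remove the difference. Montreal's catchment includes Ontario and the Maritimes, and either language is accepted at any site. The documents do not say how often language and site diverge.

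**Working it through.** **1. The plan's power figure.** Inputs from section 8: expressive means 13.6 and 20.7 with SD 8.4, so d = 7.1/8.4 = 0.845; receptive means 18.1 and 23.8 with SD 7.0, so d = 5.7/7.0 = 0.814; alpha 0.016, taken as two-sided; correlation ρ about 0.2–0.5. The symbol for the correlation is lost in the text, but the context is the ANCOVA variance factor.

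Power ≈ Φ(d/√(2v/n) − 2.409), with v = 1 − ρ² and n per group.

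| n per group | ρ | receptive | expressive |
|---|---|---|---|
| 60 | 0 | 98.0% | 98.7% |
| 60 | 0.5 | 99.7% | 99.8% |
| 30 | 0 | 77.2% | 80.6% |
| 30 | 0.2 | 79.1% | 82.4% |
| 30 | 0.5 | 89.1% | 91.5% |

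The stated floor of 80% is met with 60 per group, but the value 80% itself matches about 30 per group. The sample-size sentence calls 60 both a total and a per-group number, so both cases are carried forward.

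**2. Residual variance without a language term.** Assumptions not in the documents: within-language SD of 1, the same French shift D at both visits, equal slopes in both languages, French share p. Let w = p(1 − p)D².

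- Total variance at each visit is 1 + w and the covariance is ρ + w, so the pooled slope is (ρ + w)/(1 + w).
- Residual variance, baseline only: 1 + w − (ρ + w)²/(1 + w) = (1 − ρ)(1 + ρ + 2w)/(1 + w).
- Residual variance with a language term: 1 − ρ².
- Inflation: (1 + ρ + 2w)/[(1 + ρ)(1 + w)], which never exceeds 2/(1 + ρ).

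For D = 1:

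| p | w | ρ = 0.2 | ρ = 0.5 | ρ = 0.8 |
|---|---|---|---|---|
| 0.25 | 0.1875 | 1.575/1.425 = 1.105 | 1.875/1.781 = 1.053 | 2.175/2.1375 = 1.018 |
| 0.50 | 0.25 | 1.7/1.5 = 1.133 | 2.0/1.875 = 1.067 | 2.3/2.25 = 1.022 |

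With half French, the share of between-language variance left in the residual is (1.088 − 0.960)/0.25 = 51% at ρ = 0.2, (0.800 − 0.750)/0.25 = 20% at 0.5, and (0.368 − 0.360)/0.25 = 3% at 0.8.

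**3. Power at the plan's effect sizes** (D = 1, half French; with language term → without):

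| n per group | ρ | receptive | expressive |
|---|---|---|---|
| 60 | 0.2 | 98.4 → 96.9% | 99.0 → 97.9% |
| 60 | 0.5 | 99.7 → 99.5% | 99.8 → 99.7% |
| 30 | 0.2 | 79.1 → 73.1% | 82.4 → 76.7% |
| 30 | 0.5 | 89.1 → 86.8% | 91.5 → 89.5% |

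**4. Range over the assumed shift** (half French, expressive). With D = 0.5, inflation is 1.039 at ρ = 0.2 and 1.020 at ρ = 0.5, and the loss at 30 per group is under 2 points. With D = 2, power without the term is 95.4% (ρ = 0.2) and 99.4% (ρ = 0.5) at 60 per group, and 68.6% and 86.2% at 30 per group.

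**5. Simulation** (3,000 trials per setting, expressive effect). At 30 per group and D = 1, power was 74.1% without and 78.1% with the term at ρ = 0.2, and 87.7% and 88.6% at ρ = 0.5. The gain is somewhat smaller than the formula gives, because the formula does not charge for estimating the extra term. Type I error of the baseline-only model with D = 1 or 2 was 0.010–0.017 against a nominal 0.016, so there is no sign of inflation.

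**The case against.** The strongest reply is that the loss may be negligible.

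- Baseline already carries the language shift. The protocol says of NDW: "This measure has been shown to have excellent test-retest reliability". If that holds over 16 weeks, the 2% figure at ρ = 0.8 applies. The 0.2–0.5 correlation belongs to receptive and expressive scores that are not tied to NDW.
- The shift and the French share are assumed, and a shift near zero is possible.
- The talkativeness adjustment, not modelled above, could absorb more of any shift.
- With a true 60 per group, power stays far above 80% in every case shown.

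All of this stands, and it sets the severity. It does not remove the case for naming a variable that is fixed before treatment and can be recorded for everyone.

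A reader might infer more than the documents support:
- **That the whole language difference ends up in the error term.** It does not; baseline removes about half of the between-language variance at ρ = 0.2 and nearly all at 0.8.
- **That power falls from 80% to 74–78%.** That needs an effect of 0.52–0.59 SD, solved backwards to give exactly 80% at 60 per group. The plan's effects are 0.81–0.85.
- **That the estimate is biased.** Randomisation protects it.
- **That the plan has decided to ignore language.** It is silent.

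**Conclusion.** The point holds as a modest loss of precision. The stated model leaves in the residual whatever part of an English/French NDW difference baseline does not predict. With an assumed 1 SD shift and 25–50% French, variance inflation is about 5–13% at ρ = 0.2–0.5 and about 2% at 0.8. By the formula, the power cost at the plan's effect sizes for ρ = 0.2–0.5 is at most about 2 points with 60 per group, and about 2–6 points if 60 is the total. The true cost cannot be taken from the documents, because they give no language difference, no French share and no SD for NDW. Severity is low.

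**What to change.** In the analysis paragraph of section 8, name language of assessment (English/French) as a covariate in the primary ANCOVA, alongside baseline NDW. The cost is one sentence and one degree of freedom, with no new visits or participants. If there is in fact no language shift, the simulation puts the price at about 1 point of power or less with 30 per group (78.9% to 78.1% at ρ = 0.2; 89.5% to 88.4% at ρ = 0.5), and close to nothing with 60 per group.

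A language-specific baseline slope, a talkativeness adjustment fitted within language, and results reported by language can be listed as sensitivity analyses. They are optional: the calculation above assumes equal slopes and variances, so it supports the main effect only. The same holds for extending the rule to the Vineland editions, for which nothing was computed.

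The sample-size sentence should also state whether 60 is the total or the number per group, because the size of this loss depends on it.

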### Laboratory Evaluations:

Safety Lab Tests — At baseline and at the end of treatment/week 16 follow-up visit, comprehensive metabolic panel, glucose, vitamin B12, folate, lactate, pregnancy testing (for those female participants who are both capable of becoming pregnant and sexually active in a way that could lead to pregnancy), complete blood count, HgbA1c, and urinalysis (if able to provide a sample) will be done. A total of 3 tubes (6mL of blood) are drawn for the safety labs at each visit.

At the second visit complete metabolic panel, fasting glucose, folate, lactate, pregnancy testing, complete blood count, lipid panel (including cholesterol, LDL, and triglycerides), and urine analysis will be done.

Extension Safety labs: The same safety labs included in RCT visit 3 will be measured at 1 year and 2 years (after the beginning of the open-label extension phase).

A summary of all tests is provided below.

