### 7) Procedures Involved

At the first visit, baseline testing will include IQ testing with the Leiter-III and assessment for autism with the Autism Diagnostic Observation Scale (ADOS-2). Cognitive ability will be derived from the Leiter-III, only at baseline. We have shown that full mutation males often perform at the floor of standardized intelligence tests, such as the Wechsler Scales of intelligence, which severely restricts test sensitivity and variability, and therefore presents major limitations in analyses examining genotype-phenotype associations. The primary reason that we have chosen the Leiter-III is because it is a non-verbal test, and it can be used even with low-functioning patients who have little or no language. The ADOS-2 (Lord et al., 2000) is a semi-structured standardized assessment administered directly for the purposes of diagnosing ASD, and will be done only at baseline. The ADOS-2 uses developmentally appropriate social and object-based interactions in a 30–45 minute assessment to elicit symptoms of ASD in four areas: social interaction, communication, play, and repetitive, restrictive behaviors. The ADOS-2 consists of different modules, each directed at a particular level of language ability, and is thus appropriate to use across subjects of varying ages and functioning levels.

The CGI-S, VAS, ABC-C, ADAMS, CSHQ, SNAP-IV, PedsQL, EQ-5D, CarerQoL, Sensory Profile-2 or Sensory Profile Adolescents/Adults, ASA24, and the memory game will be completed.

Blood will also be drawn for safety laboratory tests, including a hemoglobin A1c (HgbA1c), blood glucose, complete blood count (CBC), vitamin B12 level, comprehensive metabolic panel (CMP), cholesterol, renal clearance function, blood pregnancy test for female participants in childbearing age, along with biomarker studies described below. A small skin biopsy (optional procedure) will be obtained from the back of the shoulder, utilizing a small punch biopsy after numbing the skin with lidocaine or EMLA cream, so that fibroblasts can be grown on each patient at baseline to determine the level of Fragile X Mental Retardation Protein (FMRP), the presence of tissue mosaicism, and other studies described below. At the first visit, a detailed medical history and physical and neurological examination will be carried out, with all medications and medical problems documented. A urine and stool sample will also be collected.

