### Safety Lab Tests

Chemistry	Hematology	Urinalysis		
Comprehensive Metabolic Panel:	Complete Blood Count:	Urine Dipstick Analysis:		
Light green top (3mL minimum)	Purple top (2mL minimum)	Sterile Urine Container		
Sodium	Hemoglobin	рН		
Potassium	Hematocrit	Color		
Chloride	WBC	Clarity		
Carbon Dioxide	RBC	Specific Gravity		
BUN	MCV	Occult Blood		
Creatinine	MCH	Urobilinogen		
Glucose	MCHC	Ketones		
Calcium	RDW	Protein		
Total Protein	Platelet Count	Glucose		
Albumin	Neutrophils			
ALP	Lymphocytes			
AST	Monocytes			
ALT	Eosinophils			
Total Bilirubin	Basophils			
Lipid Panel:				
Cholesterol	HgbA1c			
LDL cholesterol				
Triglyceride				
Fasting glucose				
Vitamin B12				
Folate				
Pregnancy test				
(bHCG)				
Lactate Gray top (1mL minimum)				

Molecular Biomarkers – In addition to the blood for safety labs, we will collect a minimum of 24.5 mL of blood at each visit for biomarker analysis including FMRP level, MMP9, S6 Kinase, EIF4E, *CYFIP1* mRNA, CYP450 allelic variants, proteomics, mRNA sequencing and metabolome variants. The Edmonton site will collect four EDTA tubes (2mL, 2 x 3mL, and 6mL), one PAXgene tube (2.5mL), and one CPT tubes (8mL). Due to differences in laboratory processing protocols, the Montreal site will collect 4 EDTA tubes (2mL, 3mL, and 2 x 5mL) and one PAXgene tube (2.5mL).

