#### Other, Non-Outcome Measure Procedures:

Demographics – Basic demographic information will be collected on all study subjects at the screening/baseline visit. This information includes, but is not limited to, date of birth, race, ethnicity, socioeconomic status, education of parents, parental occupation, and parental salary range.

Medical Examination – This will be carried out by the Co-PI and the nursing team at each site and may include growth percentiles, vitals, a detailed medical history, general physical and neurological examination, and review of medical records (paper, electronic), laboratory testing, and educational record, as applicable. In addition, a detailed family history may be obtained if medically necessary. A medical history and exam will be conducted at the screening/baseline visit. A medical exam and a review of recent history will take place at each subsequent visit.

The complete schedule of all study procedures is also listed in a table format below:

	Main Study			Open-label Extension		
Assessment	Visit 1 Week 1, Day 0	Visit 2 Week 8 ±7 days	Visit 3 Week 16 ± 7 days	Visit 1* Week 1	Visit 2 Week 52 ±7 days	Visit 3 Week 104 ±7 days
Informed Consent	X			X**		
Inclusion/Exclusion Criteria***	X					
Medical History	X				X	X
Physical and Neurological Exam	X	X	X	X	X	X
Vital Signs	X	X	X	X	X	X
Adverse Events a	X	X	X	X	X	X
Concomitant Medications a	X	X	X	X	X	X
Autism Diagnostic Observation Schedule (ADOS-2)	X					
Leiter-III	X				X	X
Clinical Global Impression Scale – Severity (CGI-S)	X					
Clinical Global Impression Scale – Improvement (CGI-I)		X	X	X	X	X
Anxiety Depression and Mood Scale (ADAMS)	X	X	X	X	X	X
Expressive Language Sampling (ELS)	X		X	X	X	X
Eye Tracking Measures b	X		X	X	X	X
Event Related Potential (ERP) Measures b	X		X	X	X	X
NIH Toolbox Cognitive Battery Measures b	X		X	X	X	X
Visual Analogue Scale (VAS)	X	X	X	X	X	X
Vineland Adaptive Behavior Scales—Third Edition (VABS-III)	X		X	X	X	X
Aberrant Behavior Checklist–Community (ABC-C)	X	X	X	X	X	X

Child Sleep Habits Questionnaire (CSHQ)	X	X	X	X	X	X
Swanson, Nolan and Pelham Questionnaire (SNAP-IV)	X	X	X	X	X	X
Pediatric Quality of Life (PedsQL) Parent Proxy Questionnaire	X	X	X	X	X	X
EuroQol-5D (EQ-5D)	X	X	X	X	X	X
Care Related Quality of Life (CarerQoL)	X	X	X	X	X	X
Sensory Profile-2/Sensory Profile Adolescents/Adults	X	X	X	X	X	X
Automated Self- Administered 24-Hour Dietary Assessment Tool (ASA24)	X		X	X	X	X

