The Memory Game (online) b	X		X	X	X	X
Blood Draw	X	X	X	X	X	X
Urine Collection	X	X	X	X	X	X
Stool Collection	X		X	X	X	X
Skin Biopsy (optional)	X					
Dispense Study Drug	X	X			X	
Collect Study Drug		X	X		X	X

- a: Also assessed at phone calls at Weeks 1, 2, 3, 4, and 12 and during the optional open label extension at weeks 1, 2, 3, 4, 20, 36, 52, 68, 84, 100
- b: If subject is capable of completing assessment
- \* If a participant begins the extension study within 1 year of ending the RCT portion of the study, Visit 3 of the RCT will be considered to be Visit 1 of the extension and the participant would be seen at a 1 year follow up from when they had their Visit 3 of the RCT portion. So assessments, safety laboratory and biological sample collections (blood, urine, stool) will not be duplicated if no change in medical condition has occured.
- \*\* Informed consent for the open label extension will be done at Visit 3 of the RCT portion if possible, otherwise if a participant in the RCT portion decides to participate in the open label extension later, consent will be done then.
- \*\*\* Inclusion criteria, which are met at the beginning of the RCT, will be used to participate in the open label extension as well. If a participant is over 35 by the start of the extension or any time during the extension they will still be included.

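### Two sections name different groups for the baseline pregnancy test; under the narrower one, some females capable of pregnancy receive study drug with no planned laboratory check.

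*Combined protocol and SAP*

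**What the plan says.** All references are to the Combined protocol and SAP.

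- **Section 7, Procedures Involved (first visit):** the safety bloods include a "blood pregnancy test for female participants in childbearing age". Sexual activity is not mentioned.
- **Section 7, Laboratory Evaluations (baseline and week 16):** pregnancy testing is for females who are "both capable of becoming pregnant and sexually active in a way that could lead to pregnancy".
- **Section 7, Laboratory Evaluations (visit 2):** "At the second visit complete metabolic panel, fasting glucose, folate, lactate, pregnancy testing, complete blood count" and further items are listed, with no group named for the pregnancy test.
- **Section 7, Procedures Involved (visit 2):** the fasting safety labs are defined as a lipid panel, a blood count and a metabolic panel. A pregnancy test is not among them. The same section lets visit 2 be held remotely at the investigator's discretion.
- **Safety Lab Tests table:** "Pregnancy test" (bHCG) appears with no group attached.
- **Section 4:** inclusion 2 requires females to be non-pregnant. Inclusion 3 requires contraception and accepts abstinence for those who are not sexually active. Exclusion 10 rules out pregnancy at screening. None of the three names a test.
- **Timing:** randomization follows the baseline studies, and the schedule's "Dispense Study Drug" row is marked at Visit 1.

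**The concern.** The baseline test is the last laboratory check on pregnancy before study drug is handed out. Two current sections define its population differently, so two sites could each follow the protocol and still verify exclusion 10 differently. Randomization is run separately at each site, so a difference of this kind would not necessarily come to light.

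The group that falls between the rules is females who can become pregnant and are taken not to be sexually active. The protocol does not say how sexual activity is established or by whom. Participants have an IQ of at most 85 and an age equivalent of at most 13, and many will have a caregiver answering for them. A test that depends on reported activity drops the objective check where the report may be least certain.

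At stake is exposure of an unrecognized pregnancy to study drug from the first dose.

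**Working it through.** There is no stated figure to reproduce. The check sets the texts side by side and follows one subgroup through the visits.

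**1. Who is tested at baseline.**

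| Section 7 text | Tested at baseline | Condition on sexual activity |
|---|---|---|
| Procedures Involved | females of childbearing age | none |
| Laboratory Evaluations | females capable of pregnancy and sexually active | yes |

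The safety-relevant difference is females capable of pregnancy and not considered sexually active. The first rule tests them if childbearing age, which is undefined, covers them. The second does not.

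**2. Can this subgroup enroll?** Yes. Inclusion 3 accepts abstinence for exactly these participants.

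**3. Does any other text settle the conflict?** The Safety Lab Tests table names no group. The eligibility criteria require non-pregnancy without naming a test. The schedule, introduced by "The complete schedule of all study procedures is also listed in a table format below", puts all bloods under one blood-draw row. No order of precedence between sections is given. Neither section says that a result must be known before the first dose.

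**4. When would the subgroup next be tested if Laboratory Evaluations is followed?**

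- Baseline: 0 tests.
- Week 8: undetermined. Laboratory Evaluations lists the test without saying whether the restriction carries over. Procedures Involved leaves it out of the visit 2 labs. A remote visit 2 omits the urine dipstick and research bloods, and the text does not say how safety bloods would be obtained.
- Week 16: 0 tests, because the restriction is explicit there.

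The total over the three RCT visits is therefore 0, or at most 0 + 1 + 0 = 1, and that one test would come about eight weeks after dosing began.

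**5. Assays added by one wider baseline rule.** Against Laboratory Evaluations: 1 − 0 = 1 per affected female. Against Procedures Involved: none for any female whom both terms cover. Childbearing age and capability of pregnancy are not shown to be the same group, so no general figure can be given.

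**6. Blood.** The plan states "A total of 3 tubes (6mL of blood) are drawn for the safety labs at each visit". The tube minimums in the Safety Lab Tests table are 3 mL + 2 mL + 1 mL = 6 mL, which matches, and the test is already in that table.

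**The case against.** The best defense is that the specific text refines the general one. Procedures Involved is a narrative of the visit, while Laboratory Evaluations is the dedicated section, with a detailed and apparently deliberate qualifier that fits the acceptance of abstinence. Sponsors may reasonably differ on testing participants with intellectual disability, including minors, who are reported as not sexually active. This is a fair reading, but the protocol does not state it. Even if it is right, Procedures Involved needs correcting and the subgroup still starts drug without a planned test.

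Several stronger readings are tempting, and the documents do not support them:

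- **A reader might infer that exclusion 10 is then checked by history and examination alone.** The plan says "A medical history and exam will be conducted at the screening/baseline visit", but it also allows review of records and laboratory testing as part of the medical examination, a telephone pre-screen, and chart access before consent at one site. What can be said is that no laboratory confirmation is planned for this subgroup.
- **A reader might count a definite first test at week 8.** The conflicting visit 2 lists and the remote option rule that out.
- **A reader might treat the missing pregnancy-test row in the schedule as a defect.** No individual assay has a row there, so its absence shows nothing.
- **A reader might conclude that the fix needs no extra tube, or no extra assay against Procedures Involved.** Both are plausible, but the assignment of assays to tubes cannot be fully read from the table, and childbearing age is not defined.

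**Conclusion.** The inconsistency holds. Two current sections give different populations for the same pre-dose pregnancy test, and nothing resolves them. If Laboratory Evaluations is followed, eligible females who can become pregnant but are not considered sexually active receive study drug at Visit 1 without planned laboratory confirmation of exclusion 10, and no later test is assured.

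The scope is one visit and one subgroup. Its size cannot be derived: the documents give neither the sex mix nor how many females would fall in it, and it may be small. The harm arises only where such a participant is in fact pregnant. Eligibility criteria, caregiver involvement, history and examination remain as safeguards. The consequence depends on a site following the narrower text. Sample size and the primary analysis are unaffected. A reader might infer that pregnant participants will be enrolled; the documents support only that one check is not assured. This is a minor point, worth correcting because correction is cheap.

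**What to change.** 1. **Baseline rule, stated identically in Procedures Involved and Laboratory Evaluations:** bHCG, with a negative result before the first dose, for every female participant capable of becoming pregnant, regardless of reported sexual activity. The present restriction can stay for week 16.
2. **Visit 2:** make the lists in the two sections agree on whether pregnancy testing is done and in whom.
3. **Optional:** a pregnancy-test row in the schedule.

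The wider rule is preferred because Procedures Involved already broadly plans it. If the narrower limit is deliberate, Procedures Involved should be changed to match, and the protocol should say how exclusion 10 is verified in those not tested.

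The cost is an amendment to wording in two sections, at most one extra assay per affected female compared with Laboratory Evaluations (on blood already drawn at baseline), and explaining the test to families who report no sexual activity. Requiring a negative result first also means that, for these participants, the first dose waits for the laboratory. The documents give no unit cost.
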